4.4. End of Study definition

A participant is considered to have completed the study if he/she returns for the last visit or is available for the last scheduled contact as described in the protocol. Refer to [Section 10.7.2](#) for the definition of EoS.

EoS: Last subject last visit (LSLV) of infant participants (Visit 5-NB, Day 366 post-birth)

5. STUDY POPULATION

Adherence to the inclusion and exclusion criteria specified in the protocol is essential. Deviations from these criteria are not allowed because they can jeopardize the scientific integrity, regulatory acceptability of the study or safety of the participant.

5.1. Inclusion criteria

5.1.1. Maternal participants

Maternal participants must satisfy ALL the following criteria at study entry:

- Participants who, in the opinion of the investigator, can and will comply with the requirements of the protocol (e.g. completion of diaries, return for follow-up visits).
- Participants and legally acceptable representatives (LARs) who give written or witnessed/thumb printed informed consent after the study has been explained according to local regulatory requirements, and before any study specific procedures are performed. The informed consent given at screening should (consistent with local regulations / guidelines) either:
 - include consent for both the maternal participant's participation* and participation of the infant after the infant's birth, or
 - include consent for the maternal participant's participation* and expressed willingness to consider permitting the infant to take part after the infant's birth (if local regulations/guidelines require parent(s) to provide an additional informed consent after the infant's birth).

** Written informed consent obtained from parents/LARs and written informed assent obtained from the maternal participant if she is less than legal age, or written informed consent obtained from the participant if the participant has achieved legal age. The legal age is determined according to local regulations in each participating country.*

In case the legal age is achieved during the conduct of the study, an additional written informed consent from the maternal participant should be obtained at the time of the legal age.

- both mother and father should consent if local regulations / guidelines require it.
 - Pre-pregnancy Body Mass Index (BMI) (based on participant's report) 18.5 to 39.9 kg/m², inclusive.
 - Healthy (as established by medical history and clinical examination) adolescent pregnant women, 15 to 17 YOA, inclusive, at the time of study intervention administration.
- OR
- Pregnant women, 18 to 49 YOA, inclusive, at the time of study intervention administration with:

- HIV infection (as confirmed by local standard of care serologic tests)

AND/OR

- Obstetric complications or risk factors during the current pregnancy, where the expectant management of the pregnancy is possible and without evidence of non-reassuring fetal status (only cases for which fetal heart rate can be ascertained) as follows:
 - Gestational diabetes, well-controlled on medications (with or without diet or exercise): i.e. when normoglycemia is maintained (fasting or preprandial blood glucose values <95 mg/dL [5.3 mmol/L], and/or postprandial blood glucose concentration <140 mg/dL [7.8 mmol/L] at 1 hour and/or postprandial blood glucose concentration: <120 mg/dL [6.7 mmol/L] at 2 hours).
 - Gestational hypertension, well-controlled on diet or medications below 160/110 mmHg.
 - Pre-eclampsia without severe features (i.e. eclampsia, severe hypertension [$>160/110$ mmHg], organ dysfunction, unstable or complicated by Hemolysis, Elevated Liver enzymes, and Low Platelets [HELLP] syndrome).
 - Fetal Growth Restriction in singleton pregnancies, with normal umbilical artery (UA) Doppler and estimated fetal weight 3 to 10th percentile for gestational age.
 - History of threatened preterm labor in the current pregnancy, with no cervical dilation greater than 2 cm or effacement exceeding 50%, and/or no progressive change in cervical dilation or effacement detected by serial examinations, when maternal participant is asymptomatic (i.e. no vaginal bleeding or uterine contractions or amniotic fluid loss).
 - Uncomplicated twin gestation.
- Pregnant females at 24^{0/7} to 36^{0/7} weeks of gestation at the time of study intervention administration (Day 1), as established by:
 - Last menstrual period (LMP) date corroborated by first or second trimester ultrasound examination (U/S) (i.e. at or before 28 weeks of gestation).
 - first or second trimester U/S only, if LMP is unknown/uncertain.
 - Certain LMP, corroborated by an U/S performed after 28 weeks of gestation is also acceptable.

Notes: If pregnancy resulted from assisted reproductive technologies, LMP date may be replaced by intrauterine insemination (IUI) or embryo-transfer (ET) date. Refer to Section 10.8 for guidance on gestational age assessment.

The level of diagnostic certainty of the gestational age should be established by using the GAIA gestation age assessment tool (Section 10.8).

- Participants who are willing to provide cord blood.

- Willing to have their offspring followed-up after delivery for a period of 12 months.
- Participants who do not plan to give their offspring for adoption or place the child in care.

Note that women whose pregnancies resulted from assisted reproductive technologies may be enrolled if they meet all inclusion criteria and none of the exclusion criteria.

5.1.2. Infant participants

Infant participants must satisfy all the following criteria at study entry:

- Live-born from the study pregnancy.
- If required per local regulations / guidelines, re-signed (confirmed) written or witnessed/thumb printed informed consent for study participation of the infant obtained from the infant's mother and/or father and/or LAR, before performing any infant study specific procedure. To comply with RTI surveillance and other protocol-required procedures that begin immediately after birth: if written consent cannot be provided by the parent(s)/LAR(s) readily post-birth, verbal consent – if permitted per local regulation -- may be sought from the parent(s) / LAR(s) instead. Verbal consent should be documented in the source data by the investigator or delegate. The parent(s) / LAR(s) will provide additional, written informed consent by (or before) Visit 2-NB.

5.2. Exclusion criteria

The following criteria should be checked at the time of study entry. The potential participant **MUST NOT** be included in the study if ANY exclusion criterion applies:

5.2.1. Maternal participants

5.2.1.1. Medical conditions

- History of any reaction or hypersensitivity likely to be exacerbated by any component of the study intervention.
- Hypersensitivity to latex.
- Any pre-existing medical conditions or obstetric complications in the current pregnancy that, based on the investigator's clinical judgment, are poorly controlled and/or with clinical evidence of a non-reassuring fetal status and/or are likely to result in delivery within 7 days after study intervention administration and/or when the timing of planned delivery is within 7 days after study intervention administration and/or acute conditions requiring immediate medical attention for maternal stabilization and/or treatment.
- A multiple pregnancy with 3 or more fetuses.

- Complicated twin gestation (e.g twin to twin transfusion syndrome or fetal growth restriction).
- Placenta Accreta Spectrum, including placenta increta, percreta, and accreta.
- Fetal structural defects or genetic abnormalities that affect (or are likely to affect) fetal health or survival during the first year of life.
- Known or suspected impairment of the immune system or immunodeficiency syndrome other than HIV.
- Lymphoproliferative disorder or malignancy within 5 years before study dose administration (excluding effectively treated non-melanoma skin cancer).
- Any illness of the mother or conditions of the fetus that, in the investigator's judgment, may substantially interfere with the maternal participant's ability to comply with study procedures, or could increase the risks to the mother or the fetus, or could preclude the evaluation of the participant's data.
- Any other clinical condition that, in the opinion of the investigator, might pose additional risk to the participant due to participation in the study, as determined by medical history, physical examination or laboratory screening tests.
- Women with any diagnosis, condition, treatment, or other factor that, in the opinion of the investigator, has the potential to affect or confound assessments of immunogenicity or safety
- Any conditions which, in the investigator's opinion, would increase the risks of study participation to the unborn infant.

5.2.1.2. Prior/Concomitant therapy (Amended 15 March 2022)

- Prior receipt of an RSV maternal vaccine.
- Use of any investigational or non-registered product (drug, vaccine or medical device) other than the study intervention(s) during the period beginning:
 - *For a drug, vaccine or medical device:* 29 days before the dose of study intervention(s) (Day -28 to Day 1), or their planned use during the study period.
 - *For immunoglobulins:* 90 days before the dose of study intervention(s), or their planned use during the study period.

The exception to this is investigational products (drugs / vaccines / immunoglobulins) administered in the setting of a pandemic. Administration in this case should respect the same period outlined above prior to study intervention administration, but may be allowed following delivery.

- Planned administration/administration of a vaccine not foreseen by the study protocol in the period starting 29 days before the study Day 1 and ending at delivery, with the exception of seasonal influenza vaccines, tetanus vaccines, dTpa/Tdap – alone vaccines, dTpa/Tdap vaccines that also contain other antigens and Hepatitis B vaccines, all of which may be administered according to standard of care \geq 15 days before or after study intervention (Day 1).

*Note: In case an emergency mass vaccination for an unforeseen public health threat (e.g.: a pandemic) is recommended and/or organized by the public health authorities, outside the routine immunization program, the time period described above can be reduced if necessary for that vaccine provided it is used according to the local governmental recommendations and that the Sponsor is notified accordingly. **In that sense, COVID-19 vaccines may be allowed, when administered ≥ 15 days before or after study vaccination.***

- Receipt of blood or plasma products or immunoglobulin, from 90 days before study intervention administration, or planned receipt through delivery, with the exception of Rho(D) immunoglobulin, which can be given at any time. ***In that sense, antibody therapy received against COVID-19 disease should be recorded.***
- Administration of immune-modifying therapy within 6 months before study intervention administration, or planned administration through delivery, except if it is part of management of HIV infection. This includes but is not limited to:
 - Azathioprine, mycophenolate mofetil, 6-mercaptopurine, cyclosporine, tacrolimus, monoclonal or polyclonal antibodies;
 - Prednisone ≥ 5 mg/day or equivalent for ≥ 14 days. Inhaled, intra-articular/intra-bursal and topical steroids are allowed.

5.2.1.3. Prior/Concurrent clinical study experience

- Concurrently participating in another clinical study, at any time during the study period, in which the participant has been or will be exposed to an investigational or a non-investigational intervention (drug, vaccine or invasive medical device).

Note: European Economic Community (EEC) directive 93/42/EEC defines an invasive medical device as ‘A device which, in whole or in part, penetrates inside the body, either through a body orifice or through the surface of the body’.

5.2.1.4. Other exclusions

- Alcoholism or substance use disorder within the past 24 months based on the presence of 2 or more of the following abuse criteria: hazardous use, social/interpersonal problems related to use, neglect of major roles to use, withdrawal, tolerance, use of larger amounts or longer, repeated attempts to quit or control use, much time spent using, physical or psychological problems related to use, activities given up to use, craving [[Hasin, 2013](#)].
- A local condition that in the opinion of the Investigator precludes injection of the study vaccine/product or precludes assessment of local (administration site) reactivity.
- Consanguinity of maternal participant and her partner (second degree cousins or closer).
- Any study personnel or their immediate dependants, family, or household members.

5.2.2. Infant participants

- Concurrently participating in another clinical trial, at any time during the study period, in which the participant has been or will be exposed to an investigational or a non-investigational vaccine/product (drug or invasive medical device).
- Any condition which, in the investigator's opinion, would increase the risks of study participation to the infant.
- Child in care. Please refer to Section [10.7.2](#) for the definition of child in care.

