**** Due to the change in the study requirements, RTI surveillance of the maternal participants will no longer be performed.***

Study duration for infant participants will be approximately 12 months (from birth until 365 days post-birth) which is expected to cover at least 1 complete RSV season and will be evaluated for safety and immune responses.

Blood samples for humoral immunogenicity will be collected from sub-cohorts of infant participants at Day 43, Day 121 and Day 181 post-birth*. The primary immunogenicity analysis will be based on the PPS for immunogenicity. A second analysis of

immunogenicity based on the FAS may be performed to complement the PPS analysis (Refer to Sections 9.3 and 9.4.1.2 for details).

**** Due to the change in the study requirements, there will no longer be collection of blood samples at Visit 2-NB, Visit 3-NB and Visit 4-NB.***

All infant participants born to exposed maternal participants (ES) will be followed for safety and evaluated for: neonatal/infant related AESIs up to 42 days of birth, medically assessed, RSV-associated lower respiratory tract illnesses (RSV-LRTIs) up to 365 days post-birth which is expected to cover at least 1 complete RSV season, SAEs and MAEs throughout the study period and up to the time of the last visit.

Section 4.1 provides an overview of the study design.

Safety monitoring and safety data review will be performed by an internal Safety Review Team (SRT) and an external Independent Data Monitoring Committee (IDMC).

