³ Recording will be done at Visit 1, upon maternal participant randomization but the eCRF entry will be done on the demography screen.

⁴ For safety visit or RSV-associated MA-RTI visit, eDiary entries should be reviewed only if the visit occurs between Day 1 and Day 31.

⁵ RSV-associated MA-RTI unscheduled visit should be planned if the maternal participant has any symptoms or signs as defined in Section 8.4.3.1.

⁶ **In addition to the monthly contacts between Visit-2 and the Delivery visit, additional not pre-specified contacts and/or visits can be made more often (at any desired frequency), as per investigator's, maternal participant's or LAR's discretion.**

⁷ **Due to the change in the study requirements, RTI surveillance/ assessment for the maternal participants will no longer be performed**

⁸ **Placental tissue samples will be collected at delivery from all maternal participants, whenever feasible. These samples may be tested to support possible safety assessments, if necessary. Additional details are provided in the study procedures manual (SPM).**

Note:

Contact may be via telephone, SMS, email, video-telephone/telemedicine or other means, depending on local best practice. If the study site is the participant's primary healthcare facility, contact with study personnel may also be made in the context of a visit for routine or event-driven care.

The timing of an event-driven site visit (e.g., to further evaluate a potential (S)AE or RSV-MA-RTIs) cannot be defined with precision in the protocol. Event-driven visits may occur throughout the study.

In times of special circumstances, refer to Section 8 for study procedures.

CONFIDENTIAL

214725 (RSV MAT-012)
Protocol Amendment 1 Final

Table 2 Schedule of activities (SoA) – Infant participants (Amended 15 March 2022)

Visit / Contact	V1-NB	Safety contact (recommended) 5	V2-NB	C1-NB	V3-NB	V4-NB	C2-NB	V5-NB	RTI Surveillance		Notes
									Contacts (Section 8.4.2.2.1)	Visit	
Age of infant		8 days	6 weeks	3 months	4 months	6 months	9 months	12 months			
Visit Day	Birth	D8 Post-birth	D43 Post-birth	D91 Post-birth	D121 Post-birth	D181 Post-birth	D271 Post-birth	D366 Post-birth	Birth to Day 366 Post-birth	Event-Driven	
Check inclusion / exclusion criteria	•										Sections 5.1.2 and 5.2.2
Re-consent / Consent for infant participation if required by local regulations	•										
Record infant participant study number	•										
Record sub-cohort for immunogenicity assessment	•										Section 6.3.2

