2.3. Benefit/Risk assessment (Amended 15 March 2022)

The Sponsor has included provisions in this trial to ensure participant's safety. Safety monitoring has been and will be conducted throughout this study by an unblinded Independent Data Monitoring Committee (IDMC) and by the Sponsor. The study includes the establishment of a surveillance system which may facilitate detection of respiratory tract infections, in particular lower respiratory tract infections (LRTIs) in infants enrolled in the study. Measures to suspend the study should a potential safety issue be identified are described in Section 8.2.3.

Following a recommendation from the IDMC, the Sponsor made the decision to pause the enrollment, randomization and vaccination of participants in our active pregnant women studies, including RSV MAT-012, based on an observation of imbalance of the proportion of preterm births between the vaccine group and the placebo group in the RSV MAT-009 study. This pause was to allow for an evaluation of the available data in RSV MAT-009 to better understand the safety signal observed. Following a review of additional unblinded data from this trial in which a higher proportion of neonatal deaths reported in the treatment group compared to the placebo group was also observed, the Sponsor decided to STOP enrollment and vaccination in these studies.

The safety signals are being investigated and, although at this time a cause has not been determined, the Sponsor stopped active enrollment and further vaccination of participants in the RSV MAT studies enrolling pregnant women on February 25, 2022 as a precautionary measure. The study remains ongoing for safety follow-up. Participants already vaccinated and their infants will continue to be monitored until the end of the study.

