6.3. Measures to minimize bias: randomization and blinding

6.3.1. Participant identification

Maternal identification numbers will be assigned sequentially to pregnant women who have consented to participate in the study, according to the range of participant identification numbers allocated to each study center.

Maternal participants who have provided informed consent/assent will be registered into an automated internet-based system (SBIR) at the time of screening. SBIR will be further used to confirm eligibility to participate in the study, to randomize each maternal participant to an intervention, and to confirm that an intervention has been administered (Refer to Section 6.3.3).

The maternal participant's infant (as yet unborn) will be assigned an identification number, according to the range of numbers allocated to each study center, AFTER the maternal participant has been randomized and has received the study intervention at Visit 1.

Maternal and infant identification numbers will be linked.

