**** Due to the recent safety signal, the study was fully unblinded to ensure the safety monitoring of the participants.***

The laboratory in charge of sample testing will be blinded to the study intervention assignment. Codes will be used to link the participant and study to each sample. There will be no link between the study intervention and the identity of the participant.

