3. ANALYSIS SETS

3.1. Definition

Table 3 Maternal Participants

Analysis Set	Definition / Criteria	Analyses Evaluated
Enrolled	All maternal participants who completed the informed consent process and signed the informed consent form and were determined as eligible for study participation.	Study Population
Exposed	All maternal participants who received 1 dose of a study intervention. The allocation in a group is done in function of the administered intervention.	Safety
Full Analysis Immunogenicity	All maternal participants in the Exposed set who have at least one post-dosing immunogenicity data. It will be defined by timepoint, e.g. FAS at Day 31	Immunogenicity
Per-Protocol Immunogenicity	All maternal participants in the Full Analysis (Immunogenicity) minus participants with protocol deviations that lead to exclusion. The analysis will be done according to the study interventions that participants received. It will be defined by timepoint, e.g. PPS at Day 31.	Immunogenicity
Solicited Safety	All maternal participants in the Exposed set who have solicited safety data.	Safety

FAS = Full Analysis Set; PPS = Per Protocol Set

Table 4 Infant Participants

Analysis Set	Definition / Criteria	Analyses Evaluated
Exposed	Infants live-born to exposed maternal participants, whose parents/LARs completed the informed consent process and signed the informed consent form.	Safety
Full Analysis Immunogenicity	All infant participants in the Exposed set who have at least one post-delivery/birth immunogenicity data. The analysis will be done according to the study intervention that maternal participants received. It will be defined by timepoint, e.g. FAS at Day 31	Immunogenicity
Per-Protocol Immunogenicity	All infant participants in the Full Analysis (Immunogenicity) set minus those who (a) were born less than 4 weeks post-maternal participant dosing and/ or (b) have protocol deviations that lead to exclusion. It will be defined by timepoint, e.g. PPS at Day 31	Immunogenicity

FAS = Full Analysis Set; PPS = Per Protocol Set

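### Section 5.2.2 lets an investigator refuse a live-born infant after the mother was dosed and with the arm known, and the plan neither schedules safety follow-up for refused infants nor counts them

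*Protocol*

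**What the plan says.** **The rule.** Protocol 5.2 is mandatory: a potential participant must not "be included in the study if ANY exclusion criterion applies". Section 5.2.2 gives three infant criteria: concurrent participation in another interventional trial, being a child in care, and "Any condition which, in the investigator's opinion, would increase the risks of study participation to the infant". The last has no list of conditions and no threshold.

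**The timing.** Table 2 places the row "Check inclusion / exclusion criteria" at Visit 1-NB (birth). Under Section 6.3.1 even the infant's number is assigned only once "the maternal participant has been randomized and has received the study intervention at Visit 1". After Amendment 1, Section 6.3.5 records that "the study was fully unblinded to ensure the safety monitoring of the participants", and the amendment summary gives as one reason that investigators can identify recipients. Section 5.2.2 carries no amendment mark; Section 5.2.1.2 does.

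**The promise.** Section 2.3: "Participants already vaccinated and their infants will continue to be monitored until the end of the study". Table 4 of the protocol makes infant safety to 42 days and to 365 days primary. The endpoints are SAEs, MAEs and events leading to withdrawal over both periods, with neonatal AESIs to 42 days.

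**The analysis.** SAP Table 4 defines the infant Exposed set as "Infants live-born to exposed maternal participants, whose parents/LARs completed the informed consent process and signed the informed consent form". Eligibility plays no part. SAP 3.2.1 removes infants from that set only under codes 1030, 800, 900 and 901; the infant eligibility code 2010 (SAP Table 8) affects immunogenicity only. Protocol 5.4 defines screen failures for mothers only, and the infant disposition tables (Protocol 9.4.2, SAP 6.1.1) count infants enrolled and withdrawn.

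**The concern.** This is an exclusion after randomisation, applied when the newborn's condition is visible and, for births after unblinding, when the arm is known. The conditions most likely to prompt a judgement of added risk overlap with the primary infant AESIs and with the signal from RSV MAT-009 that led to Amendment 1: preterm birth and neonatal death.

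A refused infant has no Table 2 visits or contacts. If the mother's consent already covered the infant, which Section 5.1.1 allows, the infant still meets the Exposed definition and could be tabulated as event-free. Where separate consent is needed after birth, the infant may never enter. Either way the observed event rates fall, and no table would show the reader how many infants are involved or from which arm.

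**Working it through.** **1. The plan's own figure.** Protocol 9.2.1 gives the chance of seeing at least one participant with an event among 252 vaccine recipients. The formula is 1 − (1 − p)^252. At p = 0.5%, 1% and 1.5% it gives 71.7%, 92.1% and 97.8%, against the stated 72%, 92% and 98%. It reproduces, but it makes no allowance for affected infants not being followed.

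**2. Can an infant be screened with the arm known?** The stop was on 25 February 2022 (Section 2.3). Dosing was allowed from 24 weeks. A woman dosed at 24 weeks that day would reach 40 weeks 16 weeks (112 days) later, on 17 June 2022. A pause preceded the stop, so the last doses may be earlier. Amendment 1 is dated 15 March 2022 and adds contacts before delivery and placental sampling at delivery, so births were still expected.

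**3. Effect on detection.** Let f be the share of affected infants lost through refusal. It is an assumption, since no count is given. Applying the planned 252 to infants (the number enrolled before the stop is not stated), the chance of seeing at least one event is 1 − (1 − p(1 − f))^252.

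| True rate | f = 0 | f = 10% | f = 25% | f = 50% |
|---|---|---|---|---|
| 0.5% | 71.7% | 67.9% | 61.2% | 46.8% |
| 1% | 92.1% | 89.8% | 85.0% | 71.7% |

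**4. Effect on the comparison.** Assume true rates of 7% (vaccine) and 5% (placebo): difference 2.0 points, ratio 1.40. If refused infants leave the denominator, the observed rate is p(1 − f)/(1 − pf).

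- Vaccine, f = 25%: 0.0525/0.9825 = 5.34%.
- Placebo, f = 25%: 0.0375/0.9875 = 3.80%.
- Refusal in both arms: difference about 1.5 points, ratio 1.41.
- Refusal in the vaccine arm only: 5.34% against 5%, ratio 1.07.
- Refusal in the placebo arm only: 7% against 3.80%, ratio 1.84.

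If refused infants instead stay in the denominator as event-free, the rate is p(1 − f). Loss in both arms then gives 5.25% and 3.75%: difference 1.5 points, ratio 1.40.

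So equal refusal of affected infants lowers each arm's rate and the absolute difference. The ratio moves materially only if refusal differs by arm, and then in either direction.

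**5. Is there another route for the data?** Sections 8.3.1 (Table 17, note 5), 10.1.3 and 10.3.8 have SAEs and AESIs of infants of exposed mothers reported when the site learns of them, even without infant re-consent; Section 10.3.5 says the same for AESIs. These notes do not mention infants refused under 5.2.2, set up no active follow-up and do not cover MAEs.

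**The case against.** The strongest reply is that the criterion is narrower than it looks and the data have other routes.

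- **Illness is not the test.** The condition must raise the risk of taking part. Infants receive no study product, and the Day 43, 121 and 181 bleeds have stopped. What remains is mainly examination, event-driven nasal swabs, and a birth sample only if cord blood is missing, with reduced volume for small infants. Section 5.1.2 sets no gestational-age or weight limit, and the primary AESIs include birth weight below 1000 g and death after extremely preterm birth. A reader might infer that sick newborns have to be turned away; the text does not say so.
- **Key events are partly caught elsewhere.** The reporting notes should cover deaths, preterm births and low birth weights known to the site. The mother stays in follow-up to 180 days after delivery, so a death is unlikely to go unnoticed. Pathways to preterm birth are a primary maternal endpoint, and SAP 4.3.1.2.4 counts preterm births per pregnancy.
- **Section 1.2 is not contradicted.** It says "All infant participants born to exposed maternal participants (ES) will be followed for safety", which covers infants already enrolled.
- **The Exposed set already ignores eligibility**, so its definition needs no repair.
- **Reach is limited.** Few births remained by the SAP date of 1 June 2022.

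All of this stands and narrows the point. It does not supply scheduled follow-up, MAE capture or a count for refused infants. Section 2.3 makes its statement about infants in general, so the tension there remains.

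**Conclusion.** The gap is real but moderate: a cheap improvement worth making, not a defect that must be fixed before the study can be interpreted. Live-born infants of dosed mothers can be refused on an open-ended judgement, and the plan then provides neither scheduled follow-up nor a disposition row for them. What can be lost is scheduled follow-up, MAEs, some SAEs and some neonatal AESIs. The consequence is lower observed rates and a smaller absolute difference: 2.0 to about 1.5 points under the assumed 7% and 5% with a quarter of affected infants lost in each arm.

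A reader might go further and infer that the rule biases the comparison towards no harm, for instance that 4/252 (1.6%) against 1/126 (0.8%) could shrink to 2/252 (0.8%) and the excess vanish. That requires two refusals in the vaccine arm, none in placebo, both infants dying, and neither death being picked up by a site. Open allocation permits refusal that differs by arm, but nothing in the documents shows it or its direction. Nor do they support saying that critically ill newborns are especially likely to be in another trial.

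Every rate and refusal share above is an assumption, and the arm sizes are the planned ones.

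**What to change.** 1. **Protocol 5.2.2.** For infants of mothers already dosed, state that the investigator-opinion and concurrent-trial criteria restrict only study-specific procedures (the birth blood sample and nasal swab), and not safety follow-up or data collection, subject to consent and local law.
2. **Reporting notes (Sections 8.3.1, 10.1.3, 10.3.5, 10.3.8).** Extend SAE and AESI reporting to infants refused under 5.2.2. For those already refused, obtain AESIs, SAEs and vital status from the maternal record and expedited reports where law allows.
3. **SAP 6.1.1.** Add the number of live-born infants of exposed mothers who were not enrolled, by arm and reason. Confirm that an Exposed-set infant without follow-up is not counted as event-free.

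The cost is a few sentences, one disposition row and limited record retrieval. No new procedure or participant is needed. For births already past, items 2 and 3 do most of the work.
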